#### 12.6.2 Investigator's Assessment of Clinical Response at PTE Efficacy Variable

The investigator will make an assessment of Clinical Response at the EOT and PTE Visits. The primary outcome for the EMA, Investigator's Assessment of Clinical Response at the PTE visit, is derived from the assessments at EOT and PTE visits in that a subject with a clinical response of failure at EOT is considered to have a clinical response of failure at PTE (ie, the clinical failure is carried forward) and a subject with an indeterminate response at EOT is considered to

have an indeterminate response at PTE, unless the outcome is a clinical failure at PTE. Investigator's Assessment of Clinical Response has outcomes of Clinical Success, Clinical Failure or Indeterminate (defined in Section 8.13.1.3) in the ITT population and Clinical Success and Clinical Failure in the CE population. An Indeterminate Response is included in the denominator for the calculation of the percentage of subjects with a Clinical Success in the ITT population and thus, is essentially considered a Clinical Failure for the purpose of the primary analysis for the EMA.

#### 12.6.3 Statistical Model, Hypothesis, and Method of Analysis

To demonstrate that the efficacy of omadacycline is non-inferior to moxifloxacin in the treatment of adults with CABP, the following hypothesis will be evaluated by analysis of the Clinical Success rates.

The null hypothesis and alternate hypothesis for the ECR endpoint will be assessed in the ITT population as follows:

Ho:  $\theta_T - \theta_C \leq -\Delta$ 

Hai:  $\theta_{\rm T} - \theta_{\rm C} > -\Delta$ 

Where the Clinical Success rate for the omadacycline regimen is  $\theta_T$  and for moxifloxacin is  $\theta_C$ ,

 $\Delta$  is the non-inferiority (NI) margin and is 0.10.

Similar null and alternative hypotheses can be set up with  $\Delta$  of 0.10 for the PTE endpoint. For the ECR (FDA) endpoint, a 2-sided 95% confidence interval (CI) approach for the difference of clinical success rates (using the point estimate of the difference: omadacycline response proportion minus moxifloxacin response proportion) will be used to test for the NI of the omadacycline arm compared to the moxifloxacin arm in the ITT population. The 95% CI will be calculated using the unstratified method proposed by Miettinen and Nurminen. Omadacycline will be considered non-inferior to moxifloxacin if the lower bound of the CI is greater than -0.10.

For Investigator's Assessment of Clinical Response at PTE (EMA) primary efficacy analyses in both the ITT and CE populations, a 2-sided 95% CI approach for the difference of clinical success rates (using the point estimate of the difference: omadacycline response proportion minus moxifloxacin response proportion) will be used to test for the NI of the omadacycline arm compared to the moxifloxacin arm. The 95% CI will be calculated using the stratified (for the randomization stratification factors) method proposed by Miettinen and Nurminen. Omadacycline will be considered non-inferior to moxifloxacin if the lower bound of the CI is greater than -0.10.

Early Clinical Response and Investigator's Assessment of Clinical Response at PTE will be tested separately and are not co-primary endpoints. The probability of showing NI for an ineffective drug based on PTE efficacy is 2.5%, regardless of the result for the ECRendpoint and vice versa. In addition, no alpha adjustment is needed for the co-primary efficacy endpoints for

the EMA (ITT and CE populations) since NI must be shown in both populations to conclude NI. Hence there will be no adjustment for multiple endpoints.

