## 7.8 Method of Assigning Patients to Treatment Groups

All eligible subjects will be randomized via an IxRS that assigns them to 1 of the treatment arms (in a 1:1 ratio). The site delegate will contact the IxRS after confirming that the subject fulfills all the inclusion criteria and has none of the exclusion criteria. The IxRS will assign a test article to the subject based on a computer -generated randomization schedule. The randomization will be a blocked randomization sequence stratified by PORT Risk Class (III or IV) and receipt of an allowed antibacterial (see Appendix 4) in the 72 hours prior to study treatment as defined in the

IxRS specifications and Statistical Analysis Plan (SAP). Subjects randomized into the study will be assigned the treatment corresponding to the next available number from the computergenerated randomization schedule. The subject is considered randomized when the IxRS provides the test article assignment, regardless of whether the subject actually receives any medication. Randomization of subjects who have received an allowed antibacterial therapy in the 72 hours prior to study treatment will be capped at 25% of the subjects randomized.

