### 12.6 Primary Efficacy Analysis

For all efficacy analyses, subject data will be analyzed in the group to which the subject was randomized. For the primary analyses for both the FDA and EMA, subjects will be analyzed in the stratum to which they were randomized.

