#### 12.6.4 Additional Analyses of Primary Efficacy Outcomes

Additional and sensitivity analyses of the primary efficacy outcomes (ECR and Investigator's Assessment of Clinical Response at PTE) will be performed. Analyses for the FDA primary outcome will be described here and in more detail in the SAP. Analyses for the EMA primary outcome will be described in the SAP.

If the null hypothesis of inferiority is rejected for the ECR in the ITT population and the observed success response proportion for omadacycline is larger than the observed proportion for moxifloxacin, a formal statistical analysis of superiority will be conducted. If the lower limit of the 2-sided CI for the treatment difference is greater than 0%, omadacycline will be considered superior to moxifloxacin.

The primary efficacy outcome will be assessed separately across the stratification factors of PORT Risk Class and receipt of allowed antibacterial therapy in the 72 hours prior to study treatment. For each PORT Risk Class stratum and each prior antibacterial therapy stratum, a 2-sided 95% CI for the observed difference in ECRsuccess rates will be calculated for the ITT population. Additional subgroup analyses of the primary efficacy outcome may be conducted as descriptive analyses.

Sensitivity analyses include conducting an adjusted analysis of the primary efficacy outcome based on the randomized stratum and separately, based on the stratum the subject actually belongs, and conducting an analysis where all subjects with an Indeterminate response are considered Clinical Successes.

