5.1.2 Randomization and Masking

All eligible subjects will be randomized via an Interactive Response System (IxRS) that assigns them to 1 of the 2 treatment arms omadacycline or moxifloxacin (in a 1:1 ratio). The site delegate will contact the IxRS (via web) after confirming that the subject fulfills all the inclusion criteria and has none of the exclusion criteria. The IxRS will assign a test article to the subject based on a computer-generated randomization schedule. The randomization will be a blocked randomization sequence stratified by PORT Risk Class (III and IV) and receipt of an allowed antibacterial therapy in the 72 hours prior to study treatment (yes and no). Subjects randomized into the study will be assigned the treatment corresponding to the next available number in the respective stratum of the computer-generated randomization schedule. The subject is considered randomized when the IxRS provides the test article assignment (ie, completes a randomization transaction), regardless of whether the subject actually receives any medication. Randomization of subjects who have received an allowed antibacterial therapy in the 72 hours prior to study treatment will be capped at 25% of the total number of subjects randomized.

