9 EFFICACY PARAMETERS

For all efficacy analyses, subjects will be analyzed in the group to which they were randomized. Subjects who receive the wrong test article are not included in the CE-EOT, CE-PTE, ME-EOT, and ME-PTE populations. Subjects who are randomized to the wrong PORT Risk Class or prior antibiotic stratum will be analyzed in the stratum to which they were randomized, unless otherwise stated. A summary of the efficacy analyses is provided in Appendix 2.

Subjects who miss the efficacy assessment due to COVID-19 will have an indeterminate response and the number and percentage of subjects with an indeterminate response due to COVID-19 will be summarized. Depending on the number of subjects in the study diagnosed with COVID-19, primary efficacy outcome may be analyzed in patients with and without COVID-19 and additional sensitivity analyses may be included to treat indeterminates in various ways.

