9.1 Primary Analysis

The primary efficacy analyses will be based on the ITT population. The non-inferiority test will be a 1-sided hypothesis test performed at the 2.5% level of significance. This non-inferiority test will be based on the lower limit of the 2-sided 95% confidence interval (CI). The primary efficacy outcome is the percentage of subjects with a Clinical Success at the ECR Assessment (72 to 120 hours after the first infusion of test article).

The number and percentage of subjects in each treatment group defined as an ECR Clinical Success, Clinical Failure and Indeterminate (subjects with missing data or who are lost to follow-up) will be tabulated, as will the overall category combining Clinical Failure and Indeterminate. The null and alternative hypotheses are as follows:

$$H_0: p_1 - p_2 \le -\Delta \text{ and } H_1: p_1 - p_2 > -\Delta,$$

where p_1 is the primary efficacy success rate in the omadacycline treatment group, p_2 is the primary efficacy success rate in the moxifloxacin treatment group, and Δ is the non-inferiority margin of 10%.

To test the null hypothesis, a 2-sided 95% CI for the observed difference in primary outcome rates (omadacycline treatment group minus moxifloxacin treatment group) will be calculated for the ITT population. If the lower limit of the 95% CI for the difference in the ITT population exceeds -10%, then the null hypothesis will be rejected and the non-inferiority of omadacycline to moxifloxacin will be declared.

The 2-sided 95% CI for non-inferiority testing based on the difference of ECR Clinical Success rates at the ECR assessment (72 to 120 hours after the first infusion of test article), will be computed using the method proposed without stratification by Miettinen and

Nurminen (1985). For notation purposes, assume 1 represents the omadacycline group (Group 1) and 2 represents the moxifloxacin group (Group 2).

Based on Miettinen and Nurminen, the 2-sided 95% CI is given by the roots for $RD = p_1 - p_2$ of the following equation:

$$\chi_{\alpha}^{2} = \frac{(\hat{p}_{1} - \hat{p}_{2} - RD)^{2}}{V}$$

where χ_{α}^2 is the cut point of size α from the chi-square distribution ($\chi_{\alpha}^2 = 3.84$ for 2-sided 95% CI); *RD* is the difference between the 2 true rates ($RD = p_1 - p_2$); \hat{p}_1 = the observed average proportion in Group 1; \hat{p}_2 = the observed average proportion in Group 2; and

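### The FDA primary ECR interval ignores the randomisation strata; the stratified interval already in the SAP would be a small gain at no cost in subjects (an improvement, not an error)

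*Protocol*

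**What the plan says.** **Randomisation.** Protocol 7.8: "The randomization will be a blocked randomization sequence stratified by PORT Risk Class (III or IV) and receipt of an allowed antibacterial". SAP 5.1.2 says the same: "blocked randomization sequence stratified by PORT Risk Class (III and IV) and receipt of an allowed antibacterial therapy". That makes four strata, with the prior-antibacterial share capped at 25%.

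**FDA primary (ECR, ITT).** Protocol 12.6.3: "The 95% CI will be calculated using the unstratified method proposed by Miettinen and Nurminen". SAP 9.1 has the interval "computed using the method proposed without stratification by Miettinen and" Nurminen, and links it to the Farrington-Manning test used for sizing.

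**EMA primary (PTE, ITT and CE).** The next paragraph of Protocol 12.6.3: "The 95% CI will be calculated using the stratified (for the randomization stratification factors) method proposed by Miettinen and Nurminen".

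**Stratified ECR interval.** It is planned as a sensitivity analysis. Protocol 12.6.4: "Sensitivity analyses include conducting an adjusted analysis of the primary efficacy outcome based on the randomized stratum". SAP 9.2 gives the details: stratified Miettinen-Nurminen with Cochran-Mantel-Haenszel (CMH) weights. The prior-antibacterial strata are combined if a stratum-by-arm cell has fewer than 20 subjects, or if an outcome count in such a cell is zero.

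**Stratum labels.** Protocol 12.6: "For the primary analyses for both the FDA and EMA, subjects will be analyzed in the stratum to which they were randomized". SAP 9: "Subjects who are randomized to the wrong PORT Risk Class or prior antibiotic stratum will be analyzed in the stratum to which they were" randomized. These settle which label a mis-stratified subject carries. They have no effect on an unstratified interval and do not contradict 12.6.3.

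**The concern.** Blocking within strata balances the arms on PORT class and prior antibacterial use. If those factors predict ECR, the balance reduces the true variance of the difference in success rates. An unstratified interval still uses the total variance, so it is wider than the design requires. That error is on the safe side: the cost is a little power, not false non-inferiority claims. The superiority test that follows non-inferiority is affected in the same way.

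The documents give no reason for treating the two regulators' primaries differently. Both ECR intervals are already written down, so the only question is which one decides.

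**Working it through.** **1. Reproduce the plan's power.** Inputs from Protocol 12.2 and Table 4: 80% in both arms, margin 10 points, one-sided alpha 0.025, 335 per arm. The Farrington-Manning restricted estimates at a difference of -0.10 are 0.7411 and 0.8411.
- SE under H0 = sqrt[(0.7411×0.2589 + 0.8411×0.1589)/335] = 0.03117
- SE under H1 = sqrt[2×0.8×0.2/335] = 0.03091
- Power = Φ[(0.10 − 1.960×0.03117)/0.03091] = Φ(1.259) = 89.59%, against the stated 89.6%

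The two EMA rows also reproduce (94.71% and 94.91%). By exact enumeration at 70% vs 80% with no stratum effect, the planned test has type I error 2.50%. The planned interval is sound.

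**2. Why strata can help.** With PORT IV share q, prior-antibacterial share r and additive gaps g and h, the between-stratum variance is q(1−q)g² + r(1−r)h². At q = 0.40, r = 0.25, g = 0.20, h = 0.10 it is 0.24×0.04 + 0.1875×0.01 = 0.011475. That is 7.2% of the total 0.8×0.2 = 0.16. With no gaps it is zero.

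**3. Simulation.** None of the stratum inputs is in the documents. The assumptions are 40% PORT IV, 25% prior antibacterial (the cap, not an expectation), prior antibacterial raising response, the same treatment difference in every stratum, and blocks of 4. There were 400,000 trials of 670 subjects per scenario. The stratified statistic is Σwᵢ(p̂₁ᵢ − p̂₂ᵢ + 0.10)/sqrt(Σwᵢ²Vᵢ), with wᵢ proportional to n₁ᵢn₂ᵢ/(n₁ᵢ+n₂ᵢ) and Vᵢ the Miettinen-Nurminen restricted variance. Strata were collapsed on cell size only. Type I error is taken at a true difference of -10 points. Entries are unstratified vs stratified, in %.

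| Gaps, PORT/antibacterial (points) | Power, difference 0 | Type I error | Power, control 84.3%, difference -2.2 |
|---|---|---|---|
| 0/0 | 89.74 vs 89.75 | 2.53 vs 2.53 | 76.53 vs 76.53 |
| 10/5 | 89.91 vs 90.15 | 2.42 vs 2.51 | 76.86 vs 77.24 |
| 15/5 | 90.16 vs 90.63 | 2.31 vs 2.49 | 77.09 vs 77.90 |
| 20/10 | 90.64 vs 91.47 | 2.19 vs 2.52 | 77.53 vs 78.90 |

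The Monte Carlo standard error is about 0.05 points for power near 90%, 0.07 near 77%, and 0.025 for type I error. The last column uses the CABP-1200 ECR rates in SAP Table 1 (82.1% and 84.3%).

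**4. Variations.**
- Prior antibacterial lowering response: at difference 0 and 20/10, 90.56 vs 91.43. At difference -2.2, 77.55 vs 79.10, a gain of 1.55 points and the largest at that difference.
- 25% PORT IV: gains of 0 to 0.7 points.
- 10% prior antibacterial, where strata collapse to PORT class in 99.6% of trials: 90.48 vs 91.26 at 20/10.
- A separate simulation over PORT IV shares of 25% to 50% gave gains of 0 to 0.86 points. PORT gaps of 25 and 30 points, beyond the range above, gave about 1.2 and 1.4 to 1.6.
- Superiority power at an assumed +4 points: 26.91 vs 26.96 at 0/0 and 26.14 vs 28.87 at 20/10. Stratified type I error at a difference of 0 stays between 2.45% and 2.54%.

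**5. The collapsing rule.** The smallest expected cell (PORT IV with prior antibacterial) is 335×0.40×0.25 = 33.5 per arm at the cap, 20.1 at a 15% share and 13.4 at 10%. The size rule then fires in about 0%, 47% and 99.6% of trials. Collapsing to PORT class alone keeps nearly all of the gain (91.43% vs 91.47% for four strata at 20/10). With all cells at 20 or more, the zero-count trigger fires in 0.2%, 0.4%, 1.0% and 19.1% of trials across the four rows. Dropping it costs nothing (91.46% with it, 91.47% without, at 20/10).

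**The case against.** The strongest case is that there is no deficiency to repair. Protocol and SAP agree, the interval matches the sizing method, any error is conservative, and the stratified interval will be reported anyway. The two primaries serve different regulators, the EMA analyses have their own SAP, and the FDA analyses are unstratified throughout. All of this stands, and it is why the point is an improvement only.

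The gain is also hypothetical. About 0.9 points needs the 20/10 case, a 30-point spread between best and worst stratum; 10/5 gives about 0.24. This stands too. Nor should the narrower interval be read as sample size saved. The mean half-width falls from 6.07 to 5.89 points at 20/10, which is about 40 subjects' worth of interval variance. But balanced strata already raise the unstratified test's power, and the 0.83-point gain equals only about 20 extra subjects by normal approximation.

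The zero-count trigger matters little today, because it governs only a sensitivity analysis. Its high firing rate comes from extreme cells: the 19.1% needs a 95.5% success rate in PORT III with prior antibacterial. It becomes a concern only if the stratified analysis is promoted, because the form of the primary would then depend on outcomes by arm.

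The Synopsis and SAP 5.1 name PORT class as the only stratification factor. Protocol 5.1 and 7.8 and SAP 5.1.2 are explicit about both, so this does not change the conclusion, but the wording should be aligned.

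Finally, changing a decisive analysis late invites questions about motive. That is a fair reason to act only while the data are blinded.

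**Conclusion.** The point holds as an optional improvement. The planned interval is valid and slightly conservative when the strata are prognostic. Making the stratified interval primary would add 0 to about 0.9 points of non-inferiority power at a true difference of 0, and 0 to about 1.5 points at -2.2, with type I error close to 2.5%. If neither factor predicts ECR, nothing is gained. The range rests on assumed gaps up to 20/10, an assumed PORT mix, a common treatment difference across strata and an assumed block size. None of these is given in the documents. A sponsor could reasonably keep the analysis as it is.

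**What to change.** If the database is neither locked nor unblinded:

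1. In Protocol 12.6.3 and SAP 9.1, make the stratified Miettinen-Nurminen interval of SAP 9.2 (strata as randomised, CMH weights) the primary ECR analysis. Keep the unstratified interval as a sensitivity analysis.
2. In Protocol 12.6.4 and SAP 9.2, state that the same stratified interval decides the superiority test. The current text does not name which interval applies.
3. In SAP 9.2, collapse the prior-antibacterial strata on cell size only and delete the zero-count trigger; the score interval is still defined with zero cells. The size rule can be applied blind to stratum totals. A total below 40 matched fewer than 20 in an arm in every trial simulated with blocks of 4. With blocks of 6 and a 15% prior-antibacterial share the two rules disagreed in about 2.6% of trials, so define the rule on the totals themselves.
4. Name both stratification factors in the Synopsis and SAP 5.1.

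The FDA secondary PTE intervals are descriptive and need not change.

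The cost is no extra subjects and no new method. It does need a written amendment approved by the sponsor, the IRB/IEC/REB and, where required, Health Authorities (Protocol 13.6.2), plus a new SAP version. SAP V5.0 was approved between 29 May and 5 June 2024, and the documents do not state whether the database was locked. If it is locked or unblinded, leave the primary alone and report the stratified interval as the planned sensitivity analysis.

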#### 12.6.4 Additional Analyses of Primary Efficacy Outcomes

Additional and sensitivity analyses of the primary efficacy outcomes (ECR and Investigator's Assessment of Clinical Response at PTE) will be performed. Analyses for the FDA primary outcome will be described here and in more detail in the SAP. Analyses for the EMA primary outcome will be described in the SAP.

If the null hypothesis of inferiority is rejected for the ECR in the ITT population and the observed success response proportion for omadacycline is larger than the observed proportion for moxifloxacin, a formal statistical analysis of superiority will be conducted. If the lower limit of the 2-sided CI for the treatment difference is greater than 0%, omadacycline will be considered superior to moxifloxacin.

The primary efficacy outcome will be assessed separately across the stratification factors of PORT Risk Class and receipt of allowed antibacterial therapy in the 72 hours prior to study treatment. For each PORT Risk Class stratum and each prior antibacterial therapy stratum, a 2-sided 95% CI for the observed difference in ECRsuccess rates will be calculated for the ITT population. Additional subgroup analyses of the primary efficacy outcome may be conducted as descriptive analyses.

Sensitivity analyses include conducting an adjusted analysis of the primary efficacy outcome based on the randomized stratum and separately, based on the stratum the subject actually belongs, and conducting an analysis where all subjects with an Indeterminate response are considered Clinical Successes.

### 12.7 Analysis of Secondary Variables

Analyses for the FDA secondary outcomes will be described here and in more detail in the SAP. Analyses for the EMA secondary outcomes will be described in the SAP.

The number and percentage of subjects classified as a Clinical Success, Clinical Failure and Indeterminate by the Investigator's Assessment at PTE in the ITT and CE populations (by definition subjects with an Indeterminate response are excluded from the CE population) will be calculated for each treatment group. A 2-sided unadjusted 95% CI will be constructed for the observed difference in the clinical success rate using the method of Miettinen and Nurminen. For Investigator's Assessment of Clinical Response at PTE in the ITT and CE populations (FDA secondary outcome) the 95% CI is for descriptive purposes only and no conclusion of NI will be made.

The number and percentage of subjects in each treatment group in each response category for ECRwill be presented for the microITT population. The number and percentage of subjects who are classified as a Clinical Success and Clinical Failure by the investigator at the PTE visit in ME population will be calculated. Two-sided unadjusted 95% CI will be constructed for the observed difference in the clinical success rates using the method of Miettinen and Nurminen.

The number and percentage of subjects with an ECR of success and an Investigator's Assessment of Clinical Response at PTE of Clinical Success by pathogen will be provided in the microITT and ME populations.

All-cause mortality (ACM) at 15 and 30 days after the first dose of test article will be summarized in the ITT population. Subjects who are lost to follow-up will be considered deceased for this analysis. A 2-sided unadjusted 95% CI for the observed difference in mortality rates will be calculated for ACM.

